- b. Has a pre-identified germline and/or somatic pathogenic mutation (a mutation that significantly affects the functions of genes associated with oncogenesis [NCI, 2022]) in one of the following genes: *BRCA1/2*, *PALB2*, *RAD51/51B/51C/51D*, *ATR*, *ATM*, *ARID1A*, *BAP1*, *CHEK2*, *RAD50*, *RAD54*.
 - c. Received at least 1 prior line of therapy.
 - d. Patients who have received prior PARPi are allowed **unless** they progressed within ≤ 3 months after the first dose with PARPi

Informed Consent

4. Is capable of giving signed informed consent as described in [Section 10.1.3](#), which includes compliance with the requirements and restrictions listed in the ICF and in this protocol.

Age

5. Is ≥ 18 years of age at the time of signing the informed consent.

Safety Parameters

6. Has ECOG performance status of 0 or 1.
7. Has a life expectancy of ≥ 3 months.
8. Has adequate bone marrow function, as follows:
 - a. ANC $\geq 1500/\text{mm}^3$ or $\geq 1.5 \times 10^9/\text{L}$,
 - b. Platelets $\geq 100,000/\text{mm}^3$ or $\geq 100 \times 10^9/\text{L}$,
 - c. Hemoglobin ≥ 9 g/dL (note: may have been transfused).
9. Has as adequate renal function, defined as estimated creatinine clearance ≥ 30 mL/min as calculated using the Cockcroft-Gault equation or by 24-hour urine collection for creatinine clearance or according to the local institutional standard method.
10. Has adequate liver function, as follows:
 - a. Total serum bilirubin $\leq 1.5 \times \text{ULN}$,
 - b. Aspartate aminotransferase and alanine aminotransferase $\leq 3 \times \text{ULN}$, or for participants with documented metastatic liver disease, AST and ALT levels $\leq 5 \times \text{ULN}$.

Tumor Assessment requirement

11. Has measurable disease in accordance with RECIST v1.1.

Sex and Contraceptive/Barrier Requirements

12. Male and female
 - a. **Male participants:**

Male participants are eligible to participate if they agree to the following during the study intervention period and for at least 4 months after the last dose of study intervention:

- Refrain from donating sperm.
PLUS, either:
- Be abstinent from heterosexual intercourse as their preferred and usual lifestyle (abstinent on a long-term and persistent basis) and agree to remain abstinent.
OR
- Must agree to use contraception/barrier as detailed below.

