#### 7.3.2. Creatinine Clearance (CrCL)

The creatinine clearance will be calculated using Cockcroft-Gault formula (1976), defined as:

$$CrCL(ml/min) = \frac{(140 - \text{age (in years)}) \times \text{weight (in kg)}}{72 \times \text{serum creatinine (in mg/dL)}}$$

for males and

$$CrCL(ml/min) = \frac{(140 - \text{age (in years)}) \times \text{weight (in kg)}}{72 \times \text{serum creatinine (in mg/dL)}} \times 0.85$$

for females. Baseline weight will be used.

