**Appendix 2: NCI CTCAE Criteria v5.0 for Laboratory Parameters**

PARAMETER (SI Unit)	Hypo	Hyper	ATOXGR			
			Grade 1	Grade 2	Grade 3	Grade 4
Hemoglobin (g/L)	Anemia	Hemoglobin increased	Increase in >0 - 2 g/dL	Increase in >2 - 4 g/dL	Increase in >4 g/dL	~
			Hemoglobin (Hgb) <LLN - 10.0 g/dL; <LLN - 6.2 mmol/L; <LLN - 100 g/L	Hgb <10.0 - 8.0 g/dL; <6.2 - 4.9 mmol/L; <100 - 80 g/L	Hgb <8.0 g/dL; <4.9 mmol/L; <80 g/L	~
Platelets (10  /L)	Platelet count decreased		<LLN - 75,000/mm  ; <LLN - 75.0 × 10  /L	<75,000 - 50,000/mm  ; <75.0 - 50.0 × 10  /L	<50,000 - 25,000/mm  ; <50.0 - 25.0 × 10  /L	<25,000/mm  ; <25.0 × 10  /L
Leukocytes (10  /L)	White blood cell decreased		<LLN - 3000/mm  ; <LLN - 3.0 × 10  /L	<3000 - 2000/mm  ; <3.0 - 2.0 × 10  /L	<2000 - 1000/mm  ; <2.0 - 1.0 × 10  /L	<1000/mm  ; <1.0 × 10  /L
Neutrophils (10  /L)	Neutrophil count decreased		<LLN - 1500/mm  ; <LLN - 1.5 × 10  /L	<1500 - 1000/mm  ; <1.5 - 1.0 × 10  /L	<1000 - 500/mm  ; <1.0 - 0.5 × 10  /L	<500/mm  ; <0.5 × 10  /L
Lymphocytes (10  /L)	Lymphocyte count decreased	Lymphocyte count increased	<LLN - 800/mm  ; <LLN - 0.8 × 10  /L	<800 - 500/mm  ; <0.8 - 0.5 × 10  /L	<500 - 200/mm  ; <0.5 - 0.2 × 10  /L	<200/mm  ; <0.2 × 10  /L
			~	>4000/mm  - 20,000/mm 	>20,000/mm 	~
Eosinophils (%)		Eosinophilia	>ULN and >Baseline	-	Steroids initiated	-
Activated Partial Thromboplastin Time (s)		Activated partial thromboplastin time prolonged	>ULN - 1.5 × ULN	>1.5 - 2.5 × ULN	>2.5 × ULN; bleeding	~
International Normalized Ratio		INR increased	>1.2 - 1.5	>1.5 - 2.5	>2.5	~

Jazz Pharmaceuticals, Inc.

JZP712-201 Statistical Analysis Plan - Protocol Amendment 2

PARAMETER (SI Unit)	Hypo	Hyper	ATOXGR			
			Grade 1	Grade 2	Grade 3	Grade 4
Albumin (g/L)	Hypoalbuminemia		<LLN - 3 g/dL; <LLN - 30 g/L	<3 - 2 g/dL; <30 - 20 g/L	<2 g/dL; <20 g/L	~
Glucose (mmol/L)	Hypoglycemia		<LLN - 55 mg/dL; <LLN - 3.0 mmol/L	<55 - 40 mg/dL; <3.0 - 2.2 mmol/L	<40 - 30 mg/dL; <2.2 - 1.7 mmol/L	<30 mg/dL; <1.7 mmol/L

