Creatinine (umol/L)		Creatinine increased	>ULN - 1.5 × ULN	>1.5 - 3.0 × baseline if baseline was abnormal; >1.5 - 3.0 × ULN if baseline was normal	>3.0 × baseline-6.0 × ULN if baseline was abnormal; >3.0 - 6.0 × ULN if baseline is normal	>6.0 × ULN
Creatine phosphokinase (IU/L)		CPK increased	>ULN - 2.5 × ULN	>2.5 × ULN- 5 × ULN	>5.0 X ULN - 10.0 x ULN	>10.0 × ULN
Alkaline Phosphatase (uKat/L)		Alkaline phosphatase increased	>ULN - 2.5 × ULN if baseline was normal; 2.0 - 2.5 × baseline if baseline was abnormal	>2.5 - 5.0 × ULN if baseline was normal; >2.5 - 5.0 × baseline if baseline was abnormal	>5.0 - 20.0 × ULN if baseline was normal; >5.0 - 20.0 x baseline if baseline was abnormal	>20.0 × ULN if baseline was normal; >20.0 x baseline if baseline was abnormal
Aspartate Aminotransferase (uKat/L)		Aspartate aminotransferase increased	>ULN - 3.0 × ULN if baseline was normal; 1.5 - 3.0 × baseline if baseline was abnormal	>3.0 - 5.0 × ULN if baseline was normal; >3.0 - 5.0 × baseline if baseline was abnormal	>5.0 - 20.0 × ULN if baseline was normal; >5.0 - 20.0 x baseline if baseline was abnormal	>20.0 × ULN if baseline was normal; >20.0 x baseline if baseline was abnormal
Alanine Aminotransferase (uKat/L)		Alanine aminotransferase increased	>ULN - 3.0 × ULN if baseline was normal; 1.5 - 3.0 × baseline if baseline was abnormal	>3.0 - 5.0 x ULN if baseline was normal; >3.0 - 5.0 × baseline if baseline was abnormal	>5.0 - 20.0 × ULN if baseline was normal; >5.0 - 20.0 x baseline if baseline was abnormal	>20.0 × ULN if baseline was normal; >20.0 x baseline if baseline was abnormal

Jazz Pharmaceuticals, Inc.

JZP712-201 Statistical Analysis Plan - Protocol Amendment 2

PARAMETER (SI Unit)	Hypo	Hyper	ATOXGR			
			Grade 1	Grade 2	Grade 3	Grade 4
Serum Calcium (mmol/L)	Hypocalcemia	Hypercalcemia	>ULN - 2.9 mmol/L	>2.9 - 3.1 mmol/L	>3.1 - 3.4 mmol/L	>3.4 mmol/L
			<LLN - 2.0 mmol/L	<2.0 - 1.75 mmol/L	<1.75 - 1.5 mmol/L	<1.5 mmol/L
Magnesium (mmol/L)	Hypomagnesemia	Hypermagnesemia	>ULN - 3.0 mg/dL; >ULN - 1.23 mmol/L	~	>3.0 - 8.0 mg/dL; >1.23 - 3.30 mmol/L	>8.0 mg/dL; >3.30 mmol/L
			<LLN - 1.2 mg/dL; <LLN - 0.5 mmol/L	<1.2 - 0.9 mg/dL; <0.5 - 0.4 mmol/L	<0.9 - 0.7 mg/dL; <0.4 - 0.3 mmol/L	<0.7 mg/dL; <0.3 mmol/L
Potassium (mmol/L)	Hypokalemia	Hyperkalemia	>ULN - 5.5 mmol/L	>5.5 - 6.0 mmol/L	>6.0 - 7.0 mmol/L	>7.0 mmol/L
			<LLN - 3.0 mmol/L	~	<3.0 - 2.5 mmol/L	<2.5 mmol/L

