Sodium (mmol/L)	Hyponatremia	Hypernatremia	>ULN - 150 mmol/L	>150 - 155 mmol/L	>155 - 160 mmol/L	>160 mmol/L
			<LLN - 130 mmol/L	125-129 mmol/L	120-124 mmol/L	<120 mmol/L
Bilirubin (umol/L)		Blood bilirubin increased	>ULN - 1.5 x ULN if baseline was normal; > 1.0 - 1.5 x baseline if baseline was abnormal	>1.5 - 3.0 x ULN if baseline was normal; >1.5 - 3.0 x baseline if baseline was abnormal	>3.0 - 10.0 x ULN if baseline was normal; >3.0 - 10.0 x baseline if baseline was abnormal	>10.0 x ULN if baseline was normal; >10.0 x baseline if baseline was abnormal
Urinary protein		Proteinuria	1+ proteinuria; urinary protein $\geq$ ULN - <1.0 g/24 hrs	2+ and 3+ proteinuria; urinary protein 1.0- <3.5g/24hrs	4+ proteinuria; urinary protein $\geq$ 3.5g/24hrs	~

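### The creatinine row of SAP Appendix 2 leaves some values without a grade, and gives others two, when baseline is above ULN; the haemoglobin-increase row has no stated reference

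*SAP*

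**What the plan says.** SAP Section 10.3 grades laboratory results by CTCAE v5.0 as set out in Appendix 2, and describes by cohort how many participants fall in each grade at each treatment visit.

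The Appendix 2 creatinine row reads:

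- Grade 1: above ULN up to 1.5 x ULN, with no separate rule for an abnormal baseline.
- Grade 2: ">1.5 - 3.0 × baseline if baseline was abnormal; >1.5 - 3.0 × ULN if baseline was normal".
- Grade 3: ">3.0 × baseline-6.0 × ULN if baseline was abnormal; >3.0 - 6.0 × ULN if baseline is normal".
- Grade 4: above 6.0 x ULN, whatever the baseline.

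The bilirubin row in the same table handles an abnormal baseline differently. Its Grade 1 includes "> 1.0 - 1.5 x baseline if baseline was abnormal", which meets Grade 2 at 1.5 x baseline.

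The renal entry criterion in Protocol Section 5.1 is "Has as adequate renal function, defined as estimated creatinine clearance ≥ 30 mL/min as calculated using the Cockcroft-Gault equation", or by 24-hour urine collection or the local standard method. It sets no limit on serum creatinine relative to ULN. The retreatment criteria in Protocol Section 5.5, Table 4, accept either creatinine up to 1.5 x ULN or clearance of at least 30 mL/min.

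For haemoglobin increased, Appendix 2 gives Grade 1 as "Increase in >0 - 2 g/dL", Grade 2 as a rise of more than 2 to 4 g/dL and Grade 3 as a rise of more than 4 g/dL. It names no reference value. The eosinophil row does name one (above ULN and above baseline).

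**The concern.** A grading scale should give each out-of-range value one grade, and the grade should not disappear as the value worsens. The creatinine row mixes two anchors: Grades 1 and 4 depend on ULN, while for an abnormal baseline Grade 2 and the start of Grade 3 depend on baseline. When baseline is above ULN the two anchors no longer meet.

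The programmer would then have to decide, without guidance, whether a value in the gap counts as Grade 1, Grade 2 or no grade, and which grade wins where two apply. The creatinine grade frequencies would depend on that choice. They concern participants who start with raised creatinine, for whom a reader of the safety tables would want the grading to be dependable.

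The haemoglobin row raises the same kind of question on a smaller scale: without a reference, two programmers could produce different counts from the same data.

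**Working it through.** **Inputs.** The creatinine bands are those of SAP Appendix 2. Let b be baseline divided by ULN and x the post-baseline value divided by ULN. Abnormal baseline is taken to mean b > 1.

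**Bands for b > 1, as written.** Grade 1: 1 < x ≤ 1.5. Grade 2: 1.5b < x ≤ 3b. Grade 3: 3b < x ≤ 6. Grade 4: x > 6.

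- No grade: 1.5 < x ≤ 1.5b. This is non-empty whenever b > 1.
- Grade 3 needs 3b < 6, so it is empty when b ≥ 2.
- Grades 2 and 4 both apply for 6 < x ≤ 3b (with x also above 1.5b), which needs b > 2.

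| b | No grade (x ULN) | Grade 3 (x ULN) | Grades 2 and 4 together (x ULN) |
|---|---|---|---|
| 1.1 | 1.5 to 1.65 | 3.3 to 6.0 | none |
| 1.2 | 1.5 to 1.80 | 3.6 to 6.0 | none |
| 1.4 | 1.5 to 2.10 | 4.2 to 6.0 | none |
| 1.5 | 1.5 to 2.25 | 4.5 to 6.0 | none |
| 2.0 | 1.5 to 3.00 | empty | none |
| 2.5 | 1.5 to 3.75 | empty | 6.0 to 7.5 |

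A scan of x from 1.001 to 9.000 in steps of 0.001 gave the same gaps and overlaps. With a normal baseline there was no gap and no overlap.

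**Non-monotone grading.** At b = 1.4, x = 1.45 is Grade 1, x = 1.8 has no grade and x = 2.2 is Grade 2. A fall from Grade 1 at baseline to no grade requires 1 < b ≤ 1.5. Above b = 1.5 the baseline value itself has no grade.

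**Are such baselines eligible?** Inverting the Cockcroft-Gault formula of SAP Section 7.3.2 at 30 mL/min for a man gives creatinine = (140 − age) x weight / (72 x 30).

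- Age 70, 70 kg: 70 x 70 / 2160 = 2.27 mg/dL.
- Age 60, 80 kg: 80 x 80 / 2160 = 2.96 mg/dL.

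The documents give no ULN for creatinine. Assuming 1.0 to 1.4 mg/dL, these upper limits correspond to b from 1.6 (2.27/1.4) to 3.0 (2.96/1.0). Lower values of b are eligible too. For the 70-year-old, 70 kg man at b = 1.4, creatinine is 1.40 to 1.96 mg/dL over that ULN range, and clearance is 4900/(72 x 1.40) = 48.6 down to 4900/(72 x 1.96) = 34.7 mL/min, all above 30.

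**Haemoglobin.** If the increase is measured from baseline, 9.0 to 9.5 g/dL is a rise of 0.5, hence Grade 1 increased, while 9.5 is still Grade 2 anaemia (8.0 to below 10.0). Likewise 9.0 to 13.5 is a rise of 4.5, hence Grade 3 increased. If it is measured above an assumed ULN of 16 g/dL, neither value is graded as an increase.

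**The case against.** **Having no grade is not in itself an error in this table.** For abnormal baselines, AST and ALT Grade 1 starts at 1.5 x baseline and alkaline phosphatase at 2.0 x baseline. A rise from 1.4 to 2.0 x ULN is +43% (2.0/1.4 = 1.43) and would be ungraded in those rows as well. This stands. The creatinine anomaly is narrower: a grade is given, withdrawn and given again as the value rises, and two grades can apply at once. Those other rows do not behave that way.

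**A worsening creatinine is not lost.** SAP Section 10.3 also summarises values and changes from baseline at each assessment and lists all results with reference ranges. Protocol Section 8.3.4 has investigators record clinically significant changes as adverse events, which they grade themselves. This stands, and it limits the consequence to the grade tables.

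**Stronger readings that the documents do not support:**

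- A reader might infer that the laboratory counts will be wrong. The documents give neither the number of participants with above-ULN creatinine nor the programmed rule for the gap.
- A reader might infer that any haemoglobin rise is graded as toxicity. That is only one reading, although the sole definition of laboratory change in SAP Section 10.3 (post-baseline minus baseline) makes it a plausible one. A ULN reading is equally open, and whether the row departs from the published CTCAE cannot be checked here.
- A reader might infer that recovery after transfusion would appear as an adverse laboratory shift. Section 10.3 plans frequencies per visit and no shift table.
- A reader might infer that participants at the renal entry limit drop to no grade as they worsen. At the assumed ULN range the two examples at that limit lie above b = 1.5, so their baseline has no grade to lose.

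**Conclusion.** The point holds as an incomplete grading rule. For every baseline above ULN, the creatinine row leaves the band from 1.5 x ULN to 1.5 x baseline ungraded. From 2 x ULN upward it has no Grade 3, and above 2 x ULN it assigns both Grade 2 and Grade 4 to values between 6 x ULN and 3 x baseline. These results follow from the row as written, with abnormal taken as above ULN, and no other SAP text resolves them. That such participants can enrol does not depend on one particular ULN: it holds across the assumed 1.0 to 1.4 mg/dL.

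The creatinine grade frequencies may therefore be incomplete or non-monotone for these participants. How far cannot be estimated from the documents. The haemoglobin point is secondary: a missing reference, with no demonstrated miscount.

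The primary endpoint, the cohort stopping rules and the investigator-graded AE and SAE endpoint do not use Appendix 2. This should be corrected before the laboratory tables are programmed, but it does not bear on the trial's conclusions about efficacy.

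**What to change.** **Creatinine.** Rewrite the row so that every value above ULN has exactly one grade. The normal-baseline rule can stay as it is. Two options for above-ULN baselines:

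1. Apply the baseline and ULN conditions as alternatives and assign the highest grade met. This removes both the gap and the overlap: at b = 1.4, x = 1.8 becomes Grade 2; at b = 2.5, x = 7.0 is Grade 4 only. Because 1.5b and 3b exceed 1.5 and 3.0 when b > 1, the ULN condition then always decides. The small downside is that a stable high baseline carries a grade (an unchanged 2.0 x ULN is Grade 2), so show the baseline grade alongside.
2. Extend the upper end of Grade 1 to 1.5 x baseline, following the bilirubin row. This closes the gap and keeps grading relative to baseline, but a rule for the Grade 2 and 4 overlap is still needed, and Grade 3 stays empty at b ≥ 2.

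**Haemoglobin.** State in the row whether the increase is measured from ULN or from baseline. A ULN reference avoids grading one value as both anaemia and an increase.

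**Check.** Run a fine grid of values, at several baselines, through each baseline-dependent row and confirm one grade per value.

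The cost is two table-row edits, the matching lines in the grading program and, under option 1, a baseline-grade column in the table shell. No new data are needed.
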